4.6.2.2 Presentation

All AE summaries will be presented by actual treatment group for the safety analysis set. A by- participant listing of all AEs will be provided; AEs occurring during screening will be included in the listing, but not summarized separately. The number and percentage of participants with on-treatment and on-study AEs will be tabulated separately by system organ class and preferred term. An event that occurred one or more times during a period will contribute one observation to the numerator of the proportion. The denominator of the proportion will comprise all participants in the safety population. On-treatment AEs will also be summarized by intensity/severity and separately, by causality/relatedness (as determined by the investigator). Should a participant report the same preferred term/system organ class within multiple intensity/severity or causality/relatedness categories, the participant's worst occurrence (most severe/most related) will be tabulated. Serious AEs, AEs leading to death, AEs leading to discontinuation from study intervention, and commonly occurring AEs (defined as those occurring in >5% of subjects in either treatment group) will be summarized by treatment group. AESIs will also be summarized descriptively by treatment group; serious infections will be summarized as part of the SAE by SOC and PT table in the SOC of infections and infestations and not in a separate table.

4.6.3 Clinical Laboratory, Blood Sample

4.6.3.1 Definitions and Derivations

A list of clinical chemistry and hematology variables can be found in the CSP. Baseline is defined as last available non-missing data collected prior to first dose of study intervention. Potential Hy's law definition and case confirmation are given in Appendix D of the CSP.

For results reported as lower than the LLOQ, a value equal to the LLOQ will be imputed and used for analysis purposes.

4.6.3.2 Presentations

Clinical chemistry and hematology data will be summarized by presenting shift tables and plots using normal ranges (baseline to minimum post-baseline value, baseline to maximum post-baseline value, and baseline to last observation on-study) and by presenting summary statistics of observed and change from baseline values (means, SDs, medians, quartiles, ranges). The incidence of clinically notable laboratory abnormalities will be summarized.

In order to identify potential Hy's Law cases, maximum post-baseline total bilirubin (TBL) will be plotted separately against both maximum post-baseline alanine aminotransferase (ALT) and aspartate aminotransferase (AST), expressed as multiples of the upper limit of normal (ULN). These plots will be produced on a log scale, with reference lines included at 2xULN for TBL, and at 3xULN for both ALT and AST. These plots will be produced using all data for the on-study period.

For all subjects who meet the biochemical criteria for Hy's Law (potential Hy's Law cases), the relevant laboratory variables will be tabulated showing all visits for these subjects. Subjects with elevated ALT or AST in addition to elevated TBL at any time may be explored further graphically using individual subject profile plots.

4.6.4 Clinical Laboratory, Urinalysis

4.6.4.1 Definitions and Derivations

A list of urinalysis variables can be found in the CSP. For results reported as lower than the LLOQ, a value equal to the LLOQ will be imputed and used for analysis purposes.

4.6.4.2 Presentations

Urinalysis data will be summarized by presenting shift tables (baseline to maximum post-baseline value, and baseline to last observation on-study).

4.6.5 Other Laboratory Evaluations

Not applicable.

4.6.6 Vital Signs

4.6.6.1 Definitions and Derivations

Vital signs collected include pulse rate, blood pressure, respiratory rate, and body temperature. Baseline is defined as last available non-missing data collected prior to the first dose of study intervention.

4.6.6.2 Presentations

Vital signs data will be summarized by presenting summary statistics of observed and change from baseline values by visit and treatment group. The frequency of changes (baseline to minimum post-baseline value, baseline to maximum post-baseline value, and baseline to last observation on-study) with respect to normal ranges (high/low/normal findings) will be tabulated and plotted by treatment group.

4.6.7 Electrocardiogram

4.6.7.1 Definitions and Derivations

Twelve-lead electrocardiogram (ECG) measurements are performed locally and will be recorded in accordance with the CSP at visit 1 only. The outcome of the overall evaluation

is to be recorded as normal/abnormal in the eCRF, with any abnormalities being recorded as not clinically significant or clinically significant.

4.6.7.2 Presentations

All ECG measurements will be listed, along with the overall evaluation and significance of abnormality, if applicable.

4.6.8 Other Safety Assessments

4.6.8.1 Definitions and Derivations

Any new physical exam finding(s) or aggravated existing finding(s), judged as clinically significant by the Investigator, will be reported as an AE in AE reporting.

Any device malfunctions relating to an AE, will be reported as an AE.

4.6.8.2 Presentations

Physical exam findings and device malfunctions reported as an AE will be summarized as described in section [4.6.2](#). Any reported device malfunctions will be listed.

5 INTERIM ANALYSIS

There is neither an unblinded data review nor interim analysis planned for this study prior to primary database lock.

7 APPENDIX

7.1 Appendix A: Partial Date Conventions for Adverse Events

Missing type	Action
If only the day part of the AE onset date is missing the missing day of onset of AE will be set to:	
First day of the month that the event occurred, if the onset YYYY-MM is after the YYYY-MM of first study treatmentThe day of the first study treatment, if the onset YYYY-MM is the same as YYYY-MM of the first study treatmentThe date of informed consent, if the onset YYYY-MM is before the YYYY-MM of the first treatment.
If the day and month parts of the AE onset date are missing the date of onset of AE will be set to:	
January 1 of the year of onset, if the onset year is after the year of the first study treatmentThe date of the first treatment, if the onset year is the same as the year of the first study treatmentThe date of informed consent, if the onset year is before the year of the first treatment
If only the day part of the AE resolution date is missing the missing day of resolution of AE will be set to:	The last day of the month of the occurrence. If the participant died in the same month, then set the imputed date as the death date.
If the day and month parts of the AE resolution date are missing, the date of resolution of AE will be set to:	December 31 of the year of occurrence. If the participant died in the same year, then set the imputed date as the death date.

7.2 Appendix B: Imputation Rules for Missing/Partially Missing Prior/Concomitant Medication Dates

DATE MISSING	ACTION
Completely missing start date	Assume participant had been on the medication since the date of the first study procedure.
Partially missing start date (month/year or year only)	If the partially missing onset date is the same as that for the end of study intervention treatment, it will be assumed to have started on-treatment. If the partially missing onset date is the same as that for the start of IP treatment, it will be assumed to have started before treatment. If the partially missing onset date is prior to start of IP treatment, it will be assumed to have started January 1 st if only year is present and assumed to have started the 1 st day of the respective month if year and month are present.
Completely missing end date	Assume participant had been on the medication on the date of study completion or withdrawal.
Partially missing end date (month/year or year only)	If the partially missing end date is the same as that for the start of IP treatment, it will be assumed to have ended on-treatment. If the partially missing end date is the same as that for the end of IP treatment, it will be assumed to have ended post-treatment. If the partially missing end date is after the end of IP treatment, it will be assumed to have ended December 31 st if only year is present and assumed to have ended the last day of the respective month if year and month are present.

7.3 Appendix C: Adverse events of special interest

AESIs and related definitions based on MedDRA terms are not included in this SAP to facilitate their maintenance (e.g. management of MedDRA version changes), and for convenience in using them directly in SAS programming. These detailed definitions will be finalised by the study team prior to the primary database lock and provided together with the study datasets at the time of submission.

Anaphylactic reactions

Potential anaphylactic reactions will be defined on the basis of Sampson's criteria (see [Sampson et al 2006](#)) These will be identified using a modified Standardized MedDRA Query (SMQ), with additional constraints on the timing of the AE onset date relative to the timing of the injection.

Confirmed anaphylactic reactions will be those defined following medical review of the preferred terms identified as potential anaphylactic reactions, as well as any relevant supporting data.

Guillain-Barre syndrome

Guillain-Barre syndrome will be defined using an SMQ.

Helminth infections

Helminth infection will use an investigator-driven definition, i.e. will be directly determined from what is entered on the eCRF.

A subject will be considered to have this AESI if the subject has at least one preferred term where the dedicated Helminth Infection eCRF page was also completed for that event (linked by AE number), with AE onset date during the relevant study period for analysis.

Hypersensitivity reactions

Hypersensitivity reactions will be defined using a narrow SMQ excel file according to Integrated Summary of Safety (ISS) reporting.

Immune complex disease (Type III hypersensitivity reactions)

Immune complex disease will be defined using a single PT of “Type III immune complex mediated reaction”. Since this will already be covered by the general AE reporting by SOC/PT, separate summary tables will not be needed for this AESI.

Injection site reactions

Injection site reactions will use an investigator-driven definition, i.e. will be directly determined from what is entered on the eCRF.

A subject will be considered to have this AESI if the subject has at least one preferred term with AE onset date during the relevant study period for analysis, which has “AE category” on the Adverse Events eCRF page marked as “Injection Site Reaction”.

Malignancy

Malignancy will be defined on the basis of an SMQ.

Opportunistic infections

Opportunistic infections will be defined using a pre-specified list of preferred terms (AZ defined SMQ).

Severe infections (as defined in the protocol)

Severe infections will use an investigator-driven definition, i.e. will be directly determined from what is entered on the eCRF.

A subject will be considered to have this AESI if the subject has at least one preferred term with AE onset date during the relevant study period for analysis, which satisfies the following:

- “AE Category” on Adverse Events eCRF page marked as “Severe Infection”, and one or more of the following:
 - AE is serious (“Serious” on Adverse Events eCRF page marked as “Yes”), or
 - AE required treatment with antiviral medications, intravenous antibiotics or medications for Helminth parasitic infection, or
 - AE resulted in permanent discontinuation of study drug (“Action taken, investigational product” on Adverse Events eCRF page marked as “Drug permanently discontinued”).

SIGNATURE PAGE

This is a representation of an electronic record that was signed electronically and this page is the manifestation of the electronic signature

Document Name: d5180c00031-sap-ed-2		
Document Title:	Statistical Analysis Plan Edition 2	
Document ID:	CCI [REDACTED]	
Version Label:	3.0 CURRENT LATEST APPROVED	
Server Date (dd-MMM-yyyy HH:mm 'UTC'Z)	Signed by	Meaning of Signature
28-Mar-2022 15:05 UTC	PPD [REDACTED]	Content Approval
28-Mar-2022 12:35 UTC	PPD [REDACTED]	Content Approval
28-Mar-2022 14:35 UTC	PPD [REDACTED]	Author Approval

Notes: (1) Document details as stored in CCI [REDACTED], an AstraZeneca document management system.

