To mitigate the potential risk of serious hypersensitivity reactions, during and after administration of tezepelumab, specific requirements for observing participants for AEs/SAEs and for monitoring vital signs before, during, and after administration of tezepelumab are included in the CSP. In addition, medical equipment to treat acute anaphylactic reactions will be immediately available and site staff will be trained to recognize and treat anaphylaxis.

The administration of a mAb can result in the formation of ADA. The occurrence of ADA could result in immune complex disease (Type 3 hypersensitivity reactions) with manifestations such as serum sickness, nephritis, and vasculitis, or altered tezepelumab levels or activity.

To mitigate the potential risk of immune complex disease participants will be monitored for the presence of ADA and confirmed immune complex disease through routine monitoring of AEs/SAEs. Participants with a prior history of immune complex disease will be excluded.

More detailed information about the known and expected benefits and potential risks of tezepelumab may be found in the current Investigator's Brochure.

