8.3.4 Adverse Events Based on Signs and Symptoms

All AEs spontaneously reported by the participant or care provider or reported in response to the open question from the study site staff: ‘Have you/the child had any health problems since the previous visit/you were last asked?’, or revealed by observation will be collected and recorded in the eCRF. When collecting AEs, the recording of diagnoses is preferred (when possible) to recording a list of signs and symptoms. However, if a diagnosis is known and there are other signs or symptoms that are not generally part of the diagnosis, the diagnosis and each sign or symptom will be recorded separately.

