8.3.6 Adverse Events of Special Interest

An AESI is an event of scientific and medical interest towards improving the understanding of the study intervention. An AESI may be serious or non-serious. For this study, AESIs include:

- Anaphylactic reactions
- Immune complex disease (Type 3 hypersensitivity reactions)
- Malignancy
- Helminth infections
- Severe infections which are defined as:
 - SAEs or
 - Requiring treatment with systemic antiviral medications, intravenous antibiotics or medications for helminth parasitic infection or
 - Requiring a permanent discontinuation of study intervention
- Injection site reactions
- Opportunistic infections
- Guillain-Barré Syndrome

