Immune complex disease or Hypersensitivity Type 3 is evoked by the deposition of antigen-antibody or antigen-antibody-complement complexes on cell surfaces, with subsequent involvement of breakdown products of complement, platelets, and polymorphonuclear leukocytes, and development of vasculitis; serum sickness and nephritis is common.

A 3 Signs and Symptoms and Management of Acute Anaphylaxis

Anaphylaxis is an acute and potentially lethal multi-system allergic reaction in which some or all of the following signs and symptoms occur:

- Diffuse erythema
- Pruritus
- Urticaria and/or angioedema
- Bronchospasm
- Laryngeal edema
- Hypotension
- Cardiac arrhythmias
- Feeling of impending doom
- Unconsciousness
- Shock

Other earlier or concomitant signs and symptoms can include:
Itchy nose, eyes, pharynx, genitalia, palms, and soles

- Rhinorrhea
- Change in voice
- Metallic taste
- Nausea, vomiting, diarrhea, abdominal cramps and bloating
- Light headedness
- Headache
- Uterine cramps
- Generalized warmth

A 4 Management of Acute Anaphylaxis

Immediate intervention

- 1 Assessment of airway, breathing, circulation, and adequacy of mentation
- 2 Administer epinephrine intramuscularly every 5-15 minutes, in appropriate doses, as necessary, depending on the presenting signs and symptoms of anaphylaxis, to control signs and symptoms and prevent progression to more severe symptoms such as respiratory distress, hypotension, shock and unconsciousness.

Possibly appropriate, subsequent measures depending on response to epinephrine

- (a) Place participant in recumbent position and elevate lower extremities.
- (b) Establish and maintain airway.
- (c) Administer oxygen.
- (d) Establish venous access.
- (e) Normal saline IV for fluid replacement.

Specific measures to consider after epinephrine injections, where appropriate

- (a) Consider epinephrine infusion.
- (b) Consider H₁ and H₂ antihistamines.
- (c) Consider nebulized β2 agonist [eg, albuterol (salbutamol)] for bronchospasm resistant to epinephrine.
- (d) Consider systemic corticosteroids.
- (e) Consider vasopressor (eg, dopamine).
- (f) Consider glucagon for subject taking β-blocker.
- (g) Consider atropine for symptomatic bradycardia.
- (h) Consider transportation to an emergency department or an intensive care facility.
- (i) For cardiopulmonary arrest during anaphylaxis, high-dose epinephrine and prolonged resuscitation efforts are encouraged, if necessary.

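### The SAP defines the immune complex disease AESI by one preferred term, so diagnoses of serum sickness, vasculitis or nephritis coded to other terms would not be grouped or reported as that AESI

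*SAP*

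**What the plan says.** Protocol section 8.3.6 lists immune complex disease, glossed as Type 3 hypersensitivity, among the AESIs. Section 2.3.1.2 treats it as an important potential risk linked to anti-drug antibodies: "immune complex disease (Type 3 hypersensitivity reactions) with manifestations such as serum sickness, nephritis, and vasculitis". Appendix A 2, which sets out clinical criteria for anaphylaxis and immune complex disease, again describes it by its consequences: "development of vasculitis; serum sickness and nephritis is common".

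On recording, protocol section 8.3.4 says that "the recording of diagnoses is preferred (when possible) to recording a list of signs and symptoms". Section 9.4.3.1 has AEs coded with MedDRA and the AESIs of section 8.3.6 summarised by treatment group. SAP section 4.6.2.2 repeats the AESI summary.

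SAP section 7.3 (Appendix C) then gives the operational definition: "Immune complex disease will be defined using a single PT of" *Type III immune complex mediated reaction*. Because that term already appears in the general reporting by system organ class (SOC) and preferred term (PT), the SAP concludes that "separate summary tables will not be needed for this AESI".

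**The concern.** The protocol defines the risk clinically, by what the patient develops. The SAP counts it by a single term that names the mechanism. A site that follows the recording preference may enter the clinical diagnosis, and that entry need not code to the mechanism term.

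An AESI exists to gather related events that would otherwise be scattered. If one participant had serum sickness and another vasculitis, the general tables could show each under its own term, and nothing in the planned output would present them together as possible immune complex disease. With few events expected, classifying one or two cases could change what the report says about this risk. It would also matter to the optional look at ADA status against AEs in SAP section 4.2.2.4.2, because the protocol ties this disease to ADA.

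**Working it through.** No arithmetic applies; the question is what the stated rule captures. No figure in the plan depends on it.

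**Step 1. Compare the two descriptions.**

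| Source | How immune complex disease is identified |
|---|---|
| Protocol 2.3.1.2 | Serum sickness, nephritis and vasculitis given as example manifestations |
| Protocol Appendix A 2 | Antigen-antibody deposition, with vasculitis; serum sickness and nephritis common |
| Protocol 8.3.6 | Named as a disease category, with no coded term |
| SAP 7.3 | One PT, naming the Type III mechanism |

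**Step 2. Apply the SAP rule to possible records.** Sites enter verbatim text (protocol 8.3.2), which is then coded.

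- Entry that codes to the single PT: counted as this AESI, whatever the manifestation was.
- Entry of serum sickness, coded to another PT: not counted as this AESI.
- Entry of vasculitis or nephritis, coded to another PT: not counted as this AESI.

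The second and third outcomes rest on the assumption that these diagnoses code to PTs other than the one named. The documents do not reproduce the dictionary, so this cannot be confirmed from them.

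**Step 3. Look for text that brings such events back.**

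- *General tables.* SAP 4.6.2.2 tabulates all on-treatment and on-study AEs by SOC and PT and lists all AEs by participant. The events stay visible but are not grouped.
- *Hypersensitivity AESI.* SAP sections 2 and 7.3 add this as a separate AESI with a narrow standardised query held in an external file. The file's contents are not given. It may pick up some of these events, but not under the immune complex label.
- *Definitions held outside the SAP.* Appendix C says of the MedDRA-based AESI definitions: "These detailed definitions will be finalised by the study team prior to the primary database lock". For this AESI, however, the SAP itself states the rule as one PT and rests the decision against a separate table on it. The general statement does not override that.
- *Confirmation step.* None is given for this AESI, although protocol 2.3.1.2 speaks of monitoring for confirmed immune complex disease.

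**Step 4. Compare with the other AESIs in SAP 7.3.** Of the nine AESIs there, Guillain-Barré syndrome, malignancy and hypersensitivity use standardised queries. Opportunistic infections use a pre-specified term list. Helminth infections, injection site reactions and severe infections use eCRF entries. Anaphylaxis uses a modified query and then a review: "Confirmed anaphylactic reactions will be those defined following medical review of the preferred terms identified as potential anaphylactic reactions". Immune complex disease is the only one that rests on a single PT.

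**Step 5. Check the reason for dropping the table.** The general tables replace a separate summary only if the single PT captures the disease. That is the point in doubt, so the reason does not settle it.

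**The case against.** The strongest reply is that nothing disappears. Every AE is tabulated by term and arm and listed by participant, and SAEs and AEs leading to discontinuation have their own summaries. In about 100 participants a careful reader could find a case of serum sickness. This stands. A reader might infer from the single-PT rule that the events go unreported, and the documents do not support that.

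Second, the recording preference can be read the other way. The protocol calls serum sickness, nephritis and vasculitis manifestations, names immune complex disease as an AESI and describes it in an appendix. A site might therefore record the unifying disease. That is a fair reading, so what sites would write is a prediction. The rule still has no provision for a site that records the manifestation as the diagnosis.

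Third, protocol 2.3.1.2 relies on routine AE and SAE monitoring for confirmed disease, which is broadly what the SAP does. But the SAP gives no means of confirmation and no list of candidate events to confirm.

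Fourth, a specific term avoids counting vasculitis or nephritis from other causes. That preference is legitimate, and it is why a wider list needs medical review.

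**Conclusion.** The point holds as a grouping and reporting weakness. Under the stated rule, and assuming that serum sickness, vasculitis and nephritis code to PTs other than the one named, such events would not be grouped or reported as the immune complex disease AESI. They would remain in the general AE tables and listing, and possibly in the hypersensitivity AESI.

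A reader might go further and conclude that capture is nil, or that the AESI count would read zero even if cases occurred. The documents do not support either: an event coded to the single PT would count, and which verbatim entries code there depends on a dictionary that is not shown.

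The size is modest. Few events are expected in about 100 participants, no hypothesis is tested, and the primary antibody analyses are not touched. It is still worth changing, because the rule is explicit, departs from how the protocol describes the risk, and is cheap to put right.

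**What to change.** Before the primary database lock:

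1. Replace the single PT with a pre-specified list that covers serum sickness (including serum-sickness-like reaction), vasculitis and nephritis, plus the current PT. The external definitions file that Appendix C already foresees can hold the list. The SAP text should point to it and no longer state one PT.
2. Treat events on the list as potential cases and confirm them by medical review completed before unblinding. SAP 7.3 plans medical review for anaphylaxis but does not describe it as blinded, so the blinding has to be written in. Follow-up to Week 28 continues after the primary lock, when sponsor and CRO staff learn the allocation (SAP 3.3). Any later case should be reviewed under the same criteria by someone who has not been given the treatment assignment.
3. Report potential and confirmed cases in one row by arm, and withdraw the statement that no separate summary is needed.

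The cost is a short term list, a review of probably very few events, and one table row. The downside is that vasculitis and nephritis are non-specific, so some potential cases will be reviewed and not confirmed. Showing both counts makes that visible.

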2.3 Benefit/Risk Assessment

2.3.1 Risk Assessment

Tezepelumab has been well-tolerated with no identified risks in the completed clinical studies to date. No serious allergic reactions or anaphylactic reactions causally related to tezepelumab were reported in the Phase 2 and Phase 3 studies. Although TSLP suppression could theoretically have unanticipated immune-related side effects impairing host defense against certain infections, there is no clear preclinical or clinical evidence supporting such a role, and no safety signals related to infections have been detected in the tezepelumab program.

Mild problems following inactivated influenza vaccine may include soreness, redness, or swelling where the injection was given, as well as headache (low grade), fever, muscle aches, nausea, and fatigue ([CDC Influenza 2021](#)). Very rarely, as with all vaccines, anaphylaxis may occur.

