4 STUDY DESIGN

4.1 Overall Design

This is a Phase 3b, multicenter, randomized, double-blind, parallel group, placebo-controlled study designed to investigate the potential effect of tezepelumab (210 mg SC Q4W) on antibody responses following seasonal quadrivalent influenza virus vaccination in the fall/winter 2021-2022 in the USA.

Approximately 135 participants aged 12 to 21 years with moderate to severe asthma will be enrolled into screening to provide a target sample size of approximately 100 randomized participants for the study. Participants will be randomized 1:1 to receive tezepelumab 210 mg or placebo SC Q4W, administered at Weeks 0, 4, 8 and 12. Randomization will be monitored to ensure at least 50% of the enrolled participants are between the ages of 12 to 17 years.

Treatment allocation will be stratified by age at the time of informed consent/assent (12 to 17 years, and 18 to 21 years) to ensure equitable distribution of tezepelumab and placebo treatment in the 2 age groups. To ensure that at least 50% of the enrolled participants are 12 to 17 years old, the IWRS/IVRS will be set up with a 50% cap on the 18 to 21-year age group. Once this cap is reached, no more participants will be enrolled into the 18 to 21-year age group. Once an age group is closed, participants in the screening period in the closed age group will not be allowed to be randomized and will be considered a screen failure.

After enrollment and confirmation of entry criteria, participants will enter the screening period of a minimum of 2 weeks to allow adequate time for all of the eligibility criteria to be evaluated before being randomized. Participants who meet the eligibility criteria will be randomized at Visit 3 [Week 0] and will receive either tezepelumab 210 mg or placebo by SC injection at intervals of 4 weeks, ie doses of study intervention will be administered at Weeks 0, 4, 8 and 12. The study schema is presented in [Figure 1](#).

Participants will receive a single dose of inactivated quadrivalent seasonal influenza vaccine IM at Week 12, prior to the fourth dose of study intervention. Steady-state of tezepelumab is achieved at Week 12. Serum samples for evaluation of antibody response will be drawn at Week 12 (pre-vaccination) and at Week 16 (4 weeks post-vaccination) when humoral response to the vaccination is expected to be fully developed.

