6 STUDY INTERVENTION

Study intervention is defined as any investigational intervention(s), marketed product(s) or placebo intended to be administered to a study participant according to the CSP.

In this study, administration of the inactivated quadrivalent influenza vaccine is considered a background intervention, not a study intervention.

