6.2.2.2 Dose Administration

The influenza vaccine will be administered by a qualified healthcare professional at the site at Week 12. The influenza vaccine should be injected IM, in the deltoid muscle and should be administered prior to study intervention. After influenza vaccine administration, the participant should be observed for a minimum of 15 minutes for the appearance of any acute

drug reaction and prior to administration of study intervention. A different injection site should be used for SC injection of study intervention on that day (ie, not the same upper arm). The injection sites must be recorded in the source documents and the eCRF.

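### The injection-site-reaction AESI does not separate study-injection reactions from Week 12 influenza-vaccine reactions, so vaccine reactions can be counted in it

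*SAP*

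**What the plan says.** SAP 7.3 (Appendix C) states: "Injection site reactions will use an investigator-driven definition, i.e. will be directly determined from what is entered on the eCRF". A participant counts if at least one adverse event with onset in the analysis period "has “AE category” on the Adverse Events eCRF page marked as “Injection Site Reaction". Nothing else is required. SAP 4.6.2.1 sends the reader to this appendix for AESIs derived from the eCRF. Only the definitions based on MedDRA terms are held outside the SAP, so this rule is complete as written.

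Protocol 8.3.6 gives the purpose of the category: "An AESI is an event of scientific and medical interest towards improving the understanding of the study intervention". Protocol 6 places the vaccine outside that purpose: "administration of the inactivated quadrivalent influenza vaccine is considered a background intervention, not a study intervention".

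The two injections meet at one visit. Protocol 4.1 says: "Participants will receive a single dose of inactivated quadrivalent seasonal influenza vaccine IM at Week 12, prior to the fourth dose of study intervention". Protocol 2.3.1 warns: "Mild problems following inactivated influenza vaccine may include soreness, redness, or swelling where the injection was given". Protocol 6.2.2.2 requires the two injections that day to go in different places and both sites to be entered in the eCRF. Protocol 6.2.1.3, on study-intervention dosing, adds a further eCRF page for any reported injection site reaction, but does not show its questions.

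**The concern.** A sore or swollen deltoid after the Week 12 vaccine is, in plain language, an injection site reaction. If a site records it under that category, the SAP rule accepts it on the same terms as a reaction to the subcutaneous syringe. The AESI would then mix the local tolerability of the study injection with that of a background vaccine given in both arms.

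Because the vaccine is common to the arms, mixing it in would not by itself create a difference between them. It would raise both rates and shrink the contrast, mainly on the ratio scale. If sites differ in how they use the category, the AESI also has no fixed meaning. What is at stake is how one descriptive safety table can be read.

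**Working it through.** The documents state no figure for this AESI, so there is none to reproduce. The check has two parts.

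**1. Does any text separate the two injections?**

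- *The AESI rule (SAP 7.3).* It uses a category tick and an onset date, with no condition on product, anatomical site, injection date or causality.
- *Other AESIs in the same appendix.* Anaphylaxis is identified "with additional constraints on the timing of the AE onset date relative to the timing of the injection" and then goes to medical review. Severe infections need the category plus at least one further criterion. Extra conditions are therefore used elsewhere, and this AESI has none.
- *The time window (SAP 4.6.2.1).* The on-treatment period runs to 33 days after the last dose, or to death or withdrawal if earlier. For a participant vaccinated on the day of the last dose, a local vaccine reaction in the following days falls inside it.
- *Causality (Protocol 8.3.2, SAP 4.6.2.2).* Each event is rated against the study intervention, and on-treatment events are tabulated by that rating. Neither the AESI rule nor the AESI summary uses it.
- *Instructions to sites.* No visible text says whether a vaccine-site reaction should or should not be given the category.

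The rule does not separate the two.

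**2. What would follow if vaccine reactions were recorded under the category?**

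Let *p* be the proportion with a study-injection reaction and *v* the proportion with a vaccine-site reaction recorded under the category. Take *v* as equal in both arms and independent of *p*. The counted proportion is 1 − (1 − p)(1 − v). All values of *p* and *v* below are assumptions, because the documents give none.

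Worked case, 4% on tezepelumab, 2% on placebo, v = 10%:
- Tezepelumab: 1 − 0.96 × 0.90 = 13.6%
- Placebo: 1 − 0.98 × 0.90 = 11.8%
- Ratio 13.6 / 11.8 = 1.15; difference 1.8 points

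| Assumed p (tezepelumab / placebo) | v | Counted rates | Ratio | Difference (points) |
|---|---|---|---|---|
| 4% / 2% | 0 | 4.0% / 2.0% | 2.0 | 2.0 |
| 4% / 2% | 10% | 13.6% / 11.8% | 1.15 | 1.8 |
| 4% / 2% | 30% | 32.8% / 31.4% | 1.04 | 1.4 |
| 4% / 2% | 50% | 52.0% / 51.0% | 1.02 | 1.0 |
| 10% / 2% | 0 | 10.0% / 2.0% | 5.0 | 8.0 |
| 10% / 2% | 10% | 19.0% / 11.8% | 1.61 | 7.2 |
| 10% / 2% | 30% | 37.0% / 31.4% | 1.18 | 5.6 |
| 10% / 2% | 50% | 55.0% / 51.0% | 1.08 | 4.0 |

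The difference equals the true difference times (1 − v), so it falls in proportion to *v*. The ratio falls much faster. With v = 0 nothing changes.

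**The case against.** The strongest reply is that counting depends on a form nobody outside the study team can see. The only instruction about an injection-site-reaction page sits in Protocol 6.2.1.3, under study-intervention dosing, and the vaccine section has no equivalent. That placement suggests the category may have been meant for study injections only. This stands as a reason not to claim that vaccine reactions *are* counted. It does not close the gap: the instruction names no product, and the SAP rule does not either.

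A second reply is that the AESI table only counts events by arm and attributes nothing. Causality is rated and tabulated separately, and all adverse events are listed. So a reader who infers that the plan attributes vaccine reactions to tezepelumab goes further than the documents do. But the causality table does not split this AESI by injection, so it does not resolve the mixture.

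Third, the illustration looks worst on the ratio scale, while the SAP plans no ratio for AESIs and no p-values (SAP 3.3.1). With the 50 per arm of Protocol 9.2, 4% against 2% is 2 participants against 1, which says little in any case. This stands, and it limits the importance of the point.

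Two further inferences are also unsupported. Protocol 2.3.1 says local vaccine reactions may occur and gives no frequency, so they cannot be called common on this evidence. And not everyone vaccinated at Visit 6 also gets a study injection that day: those who have discontinued study intervention can still be vaccinated there (Protocol 7.1; Table 2, footnote b).

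**Conclusion.** The point holds as a gap in definition. SAP 7.3 does not separate study-injection from vaccine-site reactions, so the latter can be counted in an AESI meant to describe the study intervention. If they are, both arms' rates rise, the ratio moves towards 1 and the absolute difference falls by the fraction *v*. This assumes equal, independent vaccine-reaction rates in the two arms.

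The actual size is unknown and may be zero. A reader might infer that the AESI rate is overstated several-fold. That would need both the assumed rates above and the recording of vaccine reactions under the category, and the documents establish neither. The effect is confined to a descriptive safety summary; the primary endpoints are untouched. This is a cheap improvement rather than a correction on which the trial's conclusions depend.

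**What to change.** In SAP 7.3, tabulate the injection-site-reaction AESI by injected product (study-injection site, vaccine site, undetermined) and by arm. Use the recorded injection sites and dates and, if it captures location, the additional reaction page. Classify undetermined events by blinded review before the primary database lock, since the sponsor and CRO learn the allocation after it.

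The documents require the injection sites to be recorded, but do not show that the location of the *reaction* is. If it was not captured, also tabulate reactions with onset before vaccination separately from those with onset on or after it. The first group cannot be due to the trial vaccine, and on the planned schedule it covers three of the four study doses (Weeks 0, 4 and 8).

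Dates are needed as well as sites. The upper arm is a permitted subcutaneous site, and only same-day use of the vaccinated arm is barred, so an earlier study dose may have gone in that arm.

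The cost is SAP wording, one derivation and blinded review of a few events. Some events may remain undetermined and should be shown as such.
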